5.3.2. Analysis Methods

Each secondary outcome will be analyzed based on time from randomization to the first occurrence in the ITT analysis set, and the Up-to-Day-45 analysis phase. The same stratified Cox model as that for the primary efficacy outcome will be used.

[figure not shown]
Other analyses described above for the primary efficacy outcome may be performed for secondary efficacy outcomes.

5.4. Multiple Testing Procedure

To control the family-wise type I error rate at alpha of 0.05 (2-sided) in testing for efficacy outcomes, if superiority of rivaroxaban over placebo on the primary efficacy outcome is established, superiority of rivaroxaban over placebo on secondary outcomes will be tested sequentially using a closed testing procedure in the hierarchical order as listed in 5.3.1, each at alpha of 0.05 (2-sided). If an individual test during any step is not statistically significant, later tests will not be declared to be statistically significant.

The following is a diagram of the multiple testing procedure.

Diagram of Multiple Testing Procedure

5.5. Other Efficacy Outcomes

5.5.1. Definition

Exploratory efficacy outcomes are:

- Symptomatic lower extremity DVT
- Symptomatic non-fatal PE
- Symptomatic upper extremity DVT
- MI
- Non-hemorrhagic stroke
- Re-hospitalization for symptomatic VTE (lower extremity DVT and non-fatal PE) within 30 days after randomization

Fatal MI or fatal stroke are defined as death occurred within 30 days of the MI or stroke and death was directly related to the MI or stroke respectively.

5.5.2. Analysis Methods

Each exploratory outcome will be summarized by treatment groups based on the ITT analysis set and Up-to-Day-45 analysis phase.

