- Re-hospitalization for symptomatic VTE (lower extremity DVT and non-fatal PE) within 30 days after randomization

Pharmacokinetic Objective

The pharmacokinetic (PK) objective is to assess the kinetics of rivaroxaban in high-risk, medically ill patients, and to describe drug exposure based on creatinine clearance (CrCl).

Medical Resource Utilization and Health Economics Objective

The medical resource utilization and health economics objective is to assess the following cost drivers, ie, re-hospitalization (including emergency room [ER] visits, intensive care unit and cardiac care unit stays), length of stay and subject discharge destination (after re-hospitalization).

Safety Objectives

The safety objectives are to compare rivaroxaban with placebo in the following bleeding outcomes in high-risk, medically ill patients:

- Major bleeding using validated International Society on Thrombosis and Haemostasis (ISTH) bleeding criteria.
- Non-major clinically relevant bleeding
- Other bleeding

Overall safety will also be assessed.

Hypotheses

The primary hypothesis is that rivaroxaban is superior to placebo in the prevention of the composite of symptomatic VTE (lower extremity DVT and non-fatal PE) and VTE-related death (death due to PE or death in which PE cannot be ruled out as the cause). The secondary hypotheses are that rivaroxaban is superior to placebo in the prevention of 1) VTE-related death (death due to PE or death in which PE cannot be ruled out as the cause), 2) symptomatic VTE (lower extremity DVT and non-fatal PE), 3) the composite of symptomatic VTE (lower extremity DVT and non-fatal PE) and ACM, 4) the composite of symptomatic VTE (lower extremity DVT and non-fatal PE), MI, non-hemorrhagic stroke and CV death (death due to a known CV cause and death in which a CV cause cannot be ruled out; by this definition, a VTE-related death is considered a CV death) and 5) ACM alone.

OVERVIEW OF STUDY DESIGN

This is a multicenter, prospective, randomized, double-blind, placebo-controlled, event-driven study designed to evaluate rivaroxaban, compared with placebo, in the prevention of symptomatic VTE (lower extremity DVT and non-fatal PE) events and VTE-related deaths (death due to PE or death in which PE cannot be ruled out as the cause) for a period of 45 days post-hospital discharge. The study consists of a screening phase, a 45-day double-blind treatment phase, and a 30-day safety follow-up period.

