1.1.4. VTE Risk Post Discharge in Patients Hospitalized for Medical Conditions

The risk of VTE persists after hospital discharge. More symptomatic VTEs have been diagnosed in the first 3 months following hospitalization than during the hospitalization phase³⁶. It has been reported that in patients hospitalized for medical conditions, the cumulative symptomatic VTE incidence from admission to 3 months was 1% and stabilizes around 50 days (Figure 1)³⁷. In this study, the median length of the hospitalization stay was 7 days.

Figure 1: Kaplan-Meier Curve Showing Cumulative Symptomatic VTE Incidence from Hospital Admission to 3 Months of Follow-up

[figure not shown]
(n=15,156; n = 143 Patients with symptomatic VTE)

Source: From Spyropoulos et al., 2011³⁷

Hull et al. (2013) demonstrated that in high risk patients 80% of the confirmed symptomatic VTE events (ie, DVT, PE) occurred within 57 days after hospital discharge and a VTE event rate of 2.7% was observed at 45 days post discharge¹⁸. Patients were classified as having VTE if the events were subsequently confirmed by diagnostic testing. High risk patients were defined as >60 years of age and having at least 1 of the following risk factors: history of malignancy, respiratory illness, neurological illness, inflammatory bowel disease, previous VTE, acute infection, or heart failure. Over the 100 day follow-up, 3.8% of the 989 patients had a confirmed VTE event (Figure 2)¹⁸.

Figure 2: Cumulative Number of Events Over Time: High-risk Elderly Medical Patients.

Source: Hull et al., 2013¹⁸

1.1.5. Studies Examining Extended Thromboprophylaxis in Patients Hospitalized for Acute Medical Conditions and MARINER Approach

While extended-duration (4-week) thromboprophylaxis has been shown to significantly reduce the incidence of VTE compared with a standard (1-week) regimen in high-risk surgical patients, extended duration thromboprophylaxis has not been shown to be of value in patients hospitalized for medical conditions. Medical patients represent most hospitalized patients and at least 75% of fatal pulmonary emboli occur in this group^{5,8,12,16,31}.

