12.3. Procedures

12.3.1. All Adverse Events

In this study, recording of only a subset of adverse events is necessary. However, any adverse event of particular concern to the investigator may be recorded in the eCRF to alert the sponsor.

The following are excluded from adverse event collection and reporting, regardless of seriousness or severity. Exempted events will be captured on the eCRF as suspected outcome events only and will be waived from unblinding and exempted from expedited reporting and include:

- VTE-related death (death due to PE or death in which PE cannot be ruled out as the cause)
- MI
- ACS
- Stroke
- TIA
- Symptomatic VTE (lower or upper extremity DVT and PE)
- Bleeding events

If the CEC determines that a suspected event does not meet the criteria for an outcome event as defined in the CEC charter, it will still be excluded from adverse event collection and reporting even if serious criteria were met.

Serious Adverse Events

All serious adverse events that are not outcome events as listed above should be reported to the sponsor as described in Section 12.3.2. While one of the efficacy outcome measures is ACM, any non-VTE-related death will be reported to the sponsor as a serious adverse event.

Certain adverse events are considered to be Adverse Events of Special Interest and should be reported as serious adverse events. These include:

- Suspected severe toxic effect on the bone marrow, such as severe thrombocytopenia (platelet count less than 50,000/ μ L), severe neutropenia (white blood cell count less than 500/ μ L), pancytopenia, aplastic anemia
- Suspected severe hypersensitivity reaction (eg, anaphylaxis, angioedema, severe urticaria, bronchospasm, etc.)
- Severe skin reactions such as Stevens-Johnson Syndrome
- Suspected severe liver injury

Non-Serious Adverse Events

The following should be reported:

- Non-serious adverse events leading to permanent study drug discontinuation
- All severe non-serious adverse events (regardless of relation to study drug) including severe laboratory abnormalities will be collected except the study outcomes.

Any other non-serious adverse events do not require reporting. However, any adverse event of particular concern to the investigator may be recorded in the eCRF to alert the sponsor.

Reporting Timelines and Processes

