An interim analysis for futility will be conducted when approximately 50% of subjects with an adjudicated primary efficacy outcome have been observed (about 50% of the expected total number of events based on the actual observed blinded pooled event rate even if this event rate is lower than the assumed rate).

Prior to randomization, all subjects must have received treatment during the index hospitalization with LMWH or UFH. The study consists of a screening phase, a 45-day double-blind treatment phase, and a 30-day follow-up. The total duration for a subject who completes the study after randomization is expected to be 75 days.

If the subject permanently discontinues treatment before Day 45, he/she should be instructed to complete an unscheduled visit and the remaining scheduled visits, including the Day 7 and Day 21 visits (if not yet completed) and the Day 45 (+4d) and Day 75 (± 5 d) visits

If a subject withdraws consent from the study or is lost to follow-up, his or her vital status and outcomes will be collected at the day 75 (± 5 d) visit either by telephone or in person, or if applicable, by a review of subject's medical or public records unless this contact is not allowed by local regulations.

For population PK analyses, based on the model performance and high variability of the PK parameters observed in the MAGELLaN study, at the Day 7 visit 2 blood samples (at pre-dose; 1-4 hours after study drug administration) and again at Day 21 visit (Visit 4) 2 blood samples (at 3 to 7 and 7 to 12 hours after study drug administration) will be collected for each subject for about 600 subjects (300 rivaroxaban subjects [200 subjects in the 10 mg QD group and 100 subjects in the 7.5 mg QD group] and 300 in the placebo group). The sparse blood samples for PK analyses will be collected in selected sites only.

An Executive Committee (EC), an Independent Data Monitoring Committee (IDMC) and a Clinical Event Committee (CEC) will be commissioned for this study.

The EC has overall responsibility for the design, conduct and reporting of the study. The EC will monitor overall safety during the study and will receive any recommendations from the IDMC regarding possible additional analyses or modifications to the study and decide whether to accept them. The EC will oversee the implementation of any modifications to the study.

[figure not shown]

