2.3. Analysis set and Analysis Phase

Each analysis involves the following 2 aspects: 1) analysis set, specifying the subjects to be included; and 2) analysis phase, specifying the time window within which data will be included.

Key analysis sets and analysis phases are defined below.

Analysis sets

- Intention-to-Treat (ITT) (as termed Full Analysis Set in the International Conference on Harmonisation [ICH] E9 guideline): This analysis set consists of all randomized subjects who have a signed valid informed consent.
- Per-Protocol (PP): This analysis set is a subset of the ITT analysis set.

Subjects with the key protocol deviations will be excluded from the PP analysis set. The categories and terms of the key protocol deviations will include the following:

- Did not meet the following inclusion or met the following exclusion criteria;
 - INT-2, INT-3, INT-4: subject with index hospitalization > 14 days, inclusion criteria 1, 2, 4, 6, exclusion criteria 10, 11, 14, 22, 24, 27
 - INT-6, INT-7: inclusion criteria 1.2, 2.2, 4.3, 6.1, exclusion criteria 10.2, 11.1, 14.1, 22.2, 24.2 without c
- Did not take any assigned study drug or took wrong study drug
- Did not discontinue study drug permanently according to the protocol (The subject becomes pregnant, develops any condition which requires permanent anticoagulation, has a fall in CrCl to below 20 mL/min during the study, or has a hemorrhagic stroke or intracranial bleeding)
- Had been taking prohibited concomitant therapies as specified in the protocol
 - INT-2: 2, 3,
 - INT-3, INT-4: 2, 3, 4, 6, 7, 8
 - INT-6, INT-7: 2.2, 3.2, 4.1, 7.1 without c and i

- Safety: This analysis set is a subset of the ITT analysis set, consisting of subjects who receive at least one dose of study drug.

Analysis phases

- Up-to-Day-45: This analysis phase includes all data from randomization to Day 45 (inclusive).

For time to event analyses, subjects who do not have events to be analyzed on or before Day 45 will be censored on Day 45 or the last outcome-evaluation date whichever occurs first.

- On-Treatment: This analysis phase includes all data from randomization to 2 days after the last dose of the study drug (inclusive).

For time to event analyses, subjects who do not have events to be analyzed during this phase will be censored on the last dose + 2 or the last outcome-evaluation date whichever occurs first.

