The following sensitivity analyses of the primary efficacy outcome will be conducted to assess the robustness of the conclusion from primary efficacy analysis: a) stratified Cox model as in the primary efficacy analysis but additionally stratified by region, b) stratified Cox model as in the primary efficacy analysis but based on the per-protocol analysis set and on-treatment analysis phase. The additional sensitivity analyses of the primary efficacy outcome may be necessary to exclude subjects (e.g., significant quality issues, GCP violations, data integrity issues, regulatory agency commitment). Additional post-hoc analyses may be conducted to investigate unexpected

results. Off-treatment primary efficacy outcome events, defined by the events from the 3 days after the last dose date, will be summarized by treatment groups.

Extensive efforts will be made to collect complete event and vital status data for all subjects randomized in this study. The amount of unavoidable missing follow-up in this study with relatively short treatment duration of 45 days is not expected to influence the conclusion from the efficacy analyses. To illustrate the extent of missingness for the primary efficacy outcome, the numbers of subjects with missing follow-up and the percentages of total missing follow-up time out of total supposed follow-up time will be summarized. A non-completer of the study will be considered as a missing follow-up subject. Missing follow-up time will be calculated by Day 45 date - last outcome-evaluation date for a missing follow-up subject. For a subject, supposed follow-up time will be calculated by minimum of [Day 45 date, death date, first primary efficacy event date] - randomization date +1. Sensitivity analyses will be conducted to estimate any additional events from the rivaroxaban and placebo group during the missing follow-up time that are needed to overturn a superiority conclusion from the primary efficacy analysis. Similar sensitivity analyses may be conducted for each component of the primary efficacy outcome.

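### Non-fatal MI, ischemic stroke, ACS, TIA and upper extremity DVT after Day 45 are collected to Day 75, but the SAP commits to no by-arm summary of them

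*SAP*

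**What the plan says.** The Protocol synopsis describes "a 45-day double-blind treatment phase, and a 30-day safety follow-up period", and SAP 1.2 states: "The total duration for a subject who completes the study after randomization is expected to be 75 days". Suspected outcomes are reviewed at the Day 75 visit (Protocol 9.1.4), outcome data are sought to that visit for every randomized subject (Protocol 10.1), and the CEC adjudicates suspected events occurring after randomization (Protocol 3.3.3).

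SAP 2.3 defines two analysis phases. Up-to-Day-45 runs from randomization through Day 45. On-Treatment runs from randomization to 2 days after the last dose. Secondary outcomes are analyzed Up-to-Day-45, and further analyses of them are optional (SAP 5.3.2). For MI, non-hemorrhagic stroke, upper extremity DVT and the other exploratory outcomes, SAP 5.5.2 says: "Each exploratory outcome will be summarized by treatment groups based on the ITT analysis set and Up-to-Day-45 analysis phase". The main benefit-risk analysis has the same window (SAP 7).

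Protocol 12.3.1 introduces a list covering VTE-related death, MI, ACS, stroke, TIA, symptomatic VTE and bleeding with: "The following are excluded from adverse event collection and reporting, regardless of seriousness or severity". The exemption stands even if the CEC does not confirm the event.

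Two by-arm outputs do reach past Day 45 for outcome events. SAP 5.2.2 promises a summary of "Off-treatment primary efficacy outcome events, defined by the events from the 3 days after the last dose date", and SAP 6.1 does the same for major bleeding.

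**The concern.** Three rules combine. The exemption keeps the listed events out of the SAE tables, the efficacy analyses stop at Day 45, and the off-treatment summaries cover only the primary outcome and major bleeding. A non-fatal MI or ischemic stroke in the follow-up month passes through all three. The protocol calls that month safety follow-up, and a by-arm difference in arterial events after an anticoagulant is stopped is one of the things it could show.

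For VTE the issue is milder. Whether treatment prevents events or partly postpones them is best judged by comparing the randomized arms cumulatively to Day 75. The plan offers instead a summary anchored on each subject's own stopping date.

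**Working it through.** **Design figure.** The plan gives no figure on this point. Its event target is defined on the Day-45 window and is not in question. It reproduces by the Schoenfeld formula: 4 × (1.960 + 1.282)² / (ln 0.6)² = 161.07, against 161 stated.

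**Step 1. Follow each event type past Day 45.**

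| Event after Day 45 | AE/SAE tables | Other committed by-arm output |
|---|---|---|
| Lower extremity DVT, non-fatal PE, VTE-related death | Exempt | Off-treatment summary (SAP 5.2.2) |
| Major bleeding, including intracranial | Exempt | Off-treatment summary (SAP 6.1) |
| Non-VTE-related death | Reported as an SAE (Protocol 12.3.1); tabulated under SAP 6.2 | ACM, to Day 45 only |
| Non-fatal MI, non-fatal ischemic stroke, upper extremity DVT | Exempt | None after Day 45 (SAP 5.5.2) |
| ACS without MI, TIA | Exempt | None; not listed as outcomes in SAP 5 |

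The last two rows are the gap.

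**Step 2. Windows for a subject whose last dose is on Day 45.**
- Outside Up-to-Day-45: 75 − 45 = 30 days, and 30/75 = 40% of planned follow-up.
- On-Treatment ends on Day 45 + 2 = Day 47.
- The off-treatment summary starts on Day 45 + 3 = Day 48 and covers 75 − 48 + 1 = 28 days. With the ±5-day window it covers 23 days (to Day 70) to 33 days (to Day 80).
- A primary event on Day 46 or 47 is in neither the ITT analysis nor the off-treatment summary. It is in the On-Treatment phase, and so in the per-protocol sensitivity analysis if the subject belongs to that set.

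**Step 3. Windows for a subject who stops on Day 5.** The off-treatment summary starts on Day 8 and covers 75 − 8 + 1 = 68 days. Of these, 45 − 8 + 1 = 38 days also lie in Up-to-Day-45, so an event on Day 20 counts in both outputs. The summary therefore pools very different windows, and who enters it early depends on stopping after randomization. The SAP gives it no end date, denominator or cumulative curve.

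**Step 4. Illustrative size, VTE only.** Protocol 1.1.4 cites a cohort of 989 high-risk patients older than 60: 2.7% VTE at 45 days, 3.8% over 100 days, and "80% of the confirmed symptomatic VTE events (ie, DVT, PE) occurred within 57 days after hospital discharge". Assume linear accrual between these points.
- By Day 57: 0.80 × 3.8% = 3.04%. Days 46–57: 3.04 − 2.70 = 0.34%.
- Days 58–75: (18/43) × (3.80 − 3.04) = 0.32%.
- Days 46–75: 0.34 + 0.32 = 0.66%, and 0.66/2.7 = 24%.
- One straight line from Day 45 to Day 100: 1.1% × 30/55 = 0.60%, and 0.60/2.7 = 22%.
- In patients: 989 × 0.60% to 0.66% is about 6 to 7, so the base is small.

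The same section cites a cohort of 15,156 whose incidence levels off around 50 days from admission. With its median stay of 7 days, that is roughly 50 − 7 = 43 days after discharge, which would leave few events after Day 45. The range is thus from few late events to about 24%.

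**The case against.** A reader might infer that a rebound or delay of VTE would not be shown by arm at all. The documents do not support that. Protocol 11.3 and SAP 5.2.2 both commit to a by-arm summary of off-treatment primary-outcome events, which are the lower extremity DVT, non-fatal PE and VTE-related death that matter most for this question. What stands is that the summary is not a comparison of the arms as randomized.

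A reader might also infer that safety is judged only on a window ending with the last dose. That is not supported either. SAP 6.1 summarizes off-treatment major bleeding, and SAP 6.2 summarizes SAEs starting more than 2 days after stopping and events with a fatal outcome. Deaths from MI or ischemic stroke would appear there. SAP 7 allows supportive benefit-risk analyses in other phases and mentions Kaplan-Meier rates over the study's duration, though it sets no end day and makes the Day-45 window primary.

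Three further points are fair. Ending the efficacy test at Day 45 matches the stated hypothesis. Output mock-ups sit in a separate Data Presentation Specifications document, so one cannot say that no such table exists, only that the SAP does not commit to one. The unblinded IDMC reviews outcome data regularly, but that is monitoring and does not put the events in the final by-arm report.

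Finally, the VTE illustration says nothing about MI or stroke. That part of the point rests on the text alone.

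**Conclusion.** The point holds in a limited form. Followed as written, the plan commits to no by-arm summary of non-fatal MI, non-fatal ischemic stroke, ACS, TIA or upper extremity DVT after Day 45, although these events are captured to Day 75 and sent for adjudication. Post-treatment VTE and major bleeding are summarized by arm, but relative to each subject's own last dose, so evidence on postponement would be weaker than the data allow; it would not be absent. Non-VTE deaths are covered by the SAE tables.

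The documents give no MI or stroke rate, so the main gap cannot be expressed in events. The 22% to 24% figure for VTE is an upper-range illustration resting on linear accrual, one older high-risk cohort and about 6 to 7 patients. The primary test, sample size and type I error are unaffected. This is a reporting improvement worth making because it is cheap.

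**What to change.** Add to SAP 2.3 a supportive, descriptive Up-to-Day-75 phase: ITT set, randomization to the Day 75 visit, censored at the last outcome-evaluation date, outside the alpha hierarchy. By randomized arm, report:

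- Kaplan-Meier curves and counts for the primary outcome, the composite of VTE, MI, non-hemorrhagic stroke and CV death, ACM, and ISTH major bleeding;
- counts of MI, non-hemorrhagic stroke and upper extremity DVT;
- Day 46–75 counts shown separately and labelled descriptive. Subjects still at risk at Day 45 are selected after randomization, so the cumulative comparison from Day 1 is the randomized one.

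At minimum, extend the off-treatment summary to MI, stroke and upper extremity DVT.

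The cost is SAP wording and a few tables, with no new visits, subjects or alpha. The Day-75 estimate may be less favourable than the Day-45 one. Ascertainment is somewhat softer late on, because the Day 75 visit has a ±5-day window, may be by telephone and has no scheduled clinical assessment. The tables should say so.
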